1 INTRODUCTION

Background

Myelodysplastic syndromes (MDS) are a heterogeneous group of clonal hematopoietic stem cell disorders characterized by ineffective hematopoiesis and variable cytopenias. As the myeloid dysplasia progresses, patients develop severe anemia requiring frequent transfusions, and develop neutropenia and thrombocytopenia from progressive bone marrow failure. About a third of patients with MDS progress to acute myeloid leukemia (AML), usually within months to years.¹

MDS is the most commonly diagnosed myeloid neoplasm in the United States. Incidence of MDS is approximately 4.6 per 100,000 people according to the SEER database. It is predominantly a disease of the elderly, with approximately 86% patients older than 60 at the time of diagnosis. The incidence of MDS is projected to increase significantly over time as a result of the aging worldwide population, increasing rates of secondary MDS in patients previously treated with chemotherapy and/or radiation for other cancers, and increased awareness of and therapeutic options for the disease.² The prognosis of MDS is generally poor, but survival ranges from a few months to many years depending on several important prognostic factors. Prognostic factors that confer poor prognosis include severe cytopenias, increased bone marrow blasts (5-20%), complex or unfavorable cytogenetics, and somatic point mutations (*TP53*, *EZH2*, *ETV6*, *RUNX1*, *ASXL1*).³⁻⁵

The treatment aims of MDS are to control symptoms, improve quality of life, improve overall survival, and decrease progression to AML. For lower risk MDS, typically supportive care with blood products and growth factors (i.e. erythropoietin, granulocyte-macrophage colony stimulating factors) are utilized.⁶ There are currently only three agents approved by the U.S. Food and Drug Administration (FDA) for the treatment of MDS: lenalidomide (Revlimid[®], Celgene Corporation), azacitidine (Vidaza[®], Celgene Corporation), and decitabine (Dacogen[®], Eisai Inc.). Lenalidomide is only approved for transfusion dependent patients with a deletion 5q cytogenetic abnormality.⁷ Azacitidine and decitabine are hypomethylating agents (HMA) approved for all MDS patients, and are typically utilized upfront for higher risk patients or for lower risk patients who have progressed on supportive care.^{8,9} Intensive chemotherapy and allogeneic stem cell transplantation are other options, however they are not suitable options for majority of elderly MDS patients due to serious and potentially fatal side effects.

The prognosis for MDS patients who fail to respond or lose their response to azacitidine or decitabine is dismal and there is a compelling unmet medical need for novel therapeutic strategies for these patients. For patients who have failed or progressed after HMA, overall survival ranges from 4-5 months in advanced patients^{10,11} and is about 15 months in low and int-1 disease (Jabbour et al, ASH 2014, abstract 388). In a recent phase III trial, the investigational agent rigosertib failed to achieve a statistically significant prolongation of overall survival versus supportive care (8.2 vs. 5.8 mos) in high-risk MDS patients who failed therapy with HMA (ASCO 2014, data in preparation) Thus, there are currently no FDA approved

agents for MDS in this setting. Hypomethylating agents azacitidine and decitabine have demonstrated single-agent efficacy in AML. In single center studies, repeated 10-day cycles of decitabine produce CR in 40-50% of newly diagnosed older patients with AML with a favorable extramedullary toxicity profile compared to standard chemotherapy.¹² Still, as with intensive chemotherapy, the median duration of remission is only 12-18 months and survival after failure of hypomethylating agent is poor. Thus, there is significant unmet need for novel agents after progression of hypomethylating agents.

1.1 THE AMINOPEPTIDASE INHIBITOR TOSEDOSTAT

1.1.1 Mechanism of Anti-leukemic Activity of Tosedostat

Tosedostat is a new orally bioavailable inhibitor of members of the M1 and M17 classes of aminopeptidases that includes the Zn²⁺-dependent aminopeptidases.¹³ Aminopeptidases catalyze the hydrolysis of the terminal amino acids from peptides or polypeptides generated by proteasomal degradation, and are involved in the continuous cycle of protein synthesis and degradation.

The aminopeptidase inhibitor tosedostat is converted in the intracellular compartment into a poorly membrane-permeable active metabolite (CHR-79888), which inhibits the M1 family of aminopeptidases, particularly puromycin-sensitive aminopeptidase and leukotriene A4 hydrolase and the M17 family member leucine aminopeptidase. Inhibition of aminopeptidases by tosedostat and its metabolite leads to an intracellular accumulation of small peptides, which in transformed cells of the hematopoietic lineage, appears to result in a deficiency of free amino acids for new protein synthesis.¹⁴ As malignant cells may be more dependent on protein cycling and availability of amino acids than the normal cells, interrupting this pathway is, therefore, a potential therapeutic target for novel agents. Microarray analysis of sensitive tumor cell lines treated with aminopeptidase inhibitors indicated that the expression of a number of genes involved in amino acid synthesis, sensing (tRNA synthetases) and transport were increased.¹⁴ These genes belong to a cohort of stress-response genes previously shown to be up-regulated in response to amino acid deprivation. In response to amino acid deprivation, the expression of pro-apoptotic proteins such as CHOP and Noxa are up-regulated, which serves to prime the cell for apoptosis and have an antiproliferative effect.¹⁵

In preclinical experiments, tosedostat exerts anti-neoplastic activity in a wide variety of cell lines *in vitro*, including solid tumor, leukemia and myeloma cell lines and has demonstrated anti-neoplastic activity in a range of *in vivo* solid tumor models.¹⁴

1.1.2 Preclinical Data on the Anti-leukemic Activity of Tosedostat

1.1.2.1 Activity of Tosedostat in AML Models *in vitro*

To determine the differential sensitivity of primary AML blasts and normal bone marrow progenitor cells to tosedostat, bone marrow samples were taken from AML patients (n=52) and controls (n=10), and the anti-proliferative effects of tosedostat were tested in a cell

proliferation assay. Tosedostat inhibited cell proliferation in the AML blast samples with a median IC₅₀ of 1.1 μ M, compared to 9 μ M in the normal bone marrow progenitor samples. Although there were no statistically significant differences between the different classes of AML, there was a trend towards a better response in the monocytic leukemias and the cytogenetic groups associated with a good prognosis.¹³

In addition to its effect on inhibiting proliferation and inducing leukemic cell apoptosis, tosedostat was found to induce differentiation of acute promyelocytic cells to mature myeloid cells.¹³

1.1.3.2 Inhibition of Endothelial Proliferation and the Anti-angiogenic Effect of Tosedostat

Endothelial cells isolated from human umbilical vein (HUVEC) were found to be very sensitive to the inhibitory effects of tosedostat; proliferation was inhibited with an IC₅₀ of 30 to 40 nM. Tosedostat has also been shown to inhibit vascular endothelial growth factor-induced angiogenesis in an *in vitro* model based on a co-culture system of HUVEC and stromal fibroblasts.¹³

1.1.3.3 Evaluation of CYP450 inhibition

Currently available *in vitro* data suggest that tosedostat may be a moderate inhibitor of selected catalytic activities of cytochrome P4503A4. Therefore, it may participate in, or contribute to, drug-drug interactions *in vivo*, which are mediated by cytochrome P4503A4.¹³

1.1.3 Aminopeptidase Inhibition in MDS: Bestatin

Bestatin is another aminopeptidase inhibitor that is utilized in oncology and hematological malignancies. It has antitumor and immunostimulant activity.¹⁶

Bestatin has been widely investigated in the clinic, albeit almost exclusively in Japan. Bestatin is approved in Japan, Korea, and China as a maintenance therapy in patients with non-lymphocytic leukemia after it was shown that it prolonged survival and remission duration, especially in elderly patients. A stimulating effect was also observed on colony forming units in culture (CFU/c). In one study, bestatin, in a daily oral dose of 30 mg, was given for as long as possible even after recurrence of disease and it prolonged overall survival, especially in the elderly Japanese population (50 to 65 years old).

Bestatin has been studied in MDS patients in Japan. In one single-arm study in MDS, 10 out of 13 patients responded after 1 month of oral therapy.¹⁶ In another study of 71MDS patients, overall response was 7%, with median duration of response 10.5 weeks.¹⁷

The clinical activity of bestatin supports aminopeptidase inhibition as a possible therapeutic approach in MDS and supports evaluation of tosedostat in MDS. Tosedostat's pharmacologic activity is improved compared to bestatin in two aspects. First, tosedostat has at least 500-fold greater anti-proliferative activity against AML cell lines than bestatin. Secondly, unlike bestatin, tosedostat is a membrane-permeable ester that is converted inside cells to an active, charged acid. The active metabolite accumulates within the cell and reaches the high

intracellular concentration required to block aminopeptidase activity.¹⁴

1.1.4 Clinical Experience with Tosedostat

1.1.4.1 Pharmacokinetic Information

Available phase I pharmacokinetic (PK) data indicate that tosedostat has a terminal half-life of 1 to 2 hours. The active metabolite CHR-79888 has a terminal half-life of between 8 and 11 hours, justifying once daily dosing. Intracellular exposure of tosedostat and CHR-79888 is good.¹³

1.1.4.2 Clinical Experience with tosedostat in hematologic malignancies

As of February 23, 2014, there have been two published studies of tosedostat in hematologic malignancies.

CHR-2797-002 was a phase I-II study to evaluate the safety, tolerability and anti-disease activity of the aminopeptidase inhibitor tosedostat, in elderly and/or treatment refractory subjects with acute myeloid leukemia (AML), myelodysplastic syndrome (MDS) or multiple myeloma (MM).¹⁸ In the study, 51 subjects had AML, 4 had MDS, and 2 had MM. In the phase I portion, four of 13 AML patients (31%), two at 60mg and two at 130mg, achieved complete marrow responses. Among the 4 subjects with high risk MDS, one subject met the criteria of stable disease and another subject reached a partial response with a complete morphological bone marrow response. These responses were evident at the end of treatment and confirmed 12 weeks later. In addition, 1 of 2 subjects with MM achieved stable disease at the end of the study, which was confirmed 3 months later.¹⁸

The dose of tosedostat selected in phase I of CHR-2797-002 was 130 mg. This was based on the occurrence of one DLT of raised alanine aminotransferase (ALT) (grade 3) at 130 mg and 2 cases of thrombocytopenia (grade 4) at 180 mg. On the basis of these results, 130mg was considered to be a suitable dose for ongoing or maintenance treatment of AML subjects.¹⁸

Overall, in the CHR-2797-002 study, 7 out of 51 AML (2 on 60 mg, and 5 on 130 mg) subjects had a reduction in bone marrow blast counts (<5% blastocytes) and achieved a complete response, at some stage during the study. One of the 7 responders (on 60 mg) had a fibrotic bone marrow but became completely transfusion independent and had a hypocellular bone marrow sample suggestive of a complete response, and is counted as such. Four of the AML complete responders also showed hematological recovery, with recovery of neutrophils, platelets and hemoglobin, such that they met the criteria for a complete remission of their AML (duration of complete remission between 4 and 11 months). Seven further AML subjects had reductions in bone marrow blast counts (between 5 and 15% blastocytes) and achieved a partial response, at some stage during the study. Two of these were short duration responses, noted during treatment, whilst 5 subjects remained on treatment, and the responses lasted until 4 to 12 weeks after the end of the protocol-defined treatment period.¹⁸

The OPAL study was a randomized open-label phase II study that evaluated tosedostat in

elderly (≥ 60 years) AML patients who had relapsed after achieving first complete remission lasting less than 12 months or who had not achieved previous complete remission. One cohort received tosedostat at 120mg once daily for 6 months, and the other cohort received tosedostat for 240mg once daily for 2 months followed by 120mg for 4 months. Overall, seven patients (10%) had complete remission or complete remission with incomplete platelet recovery; two in the 120mg cohort and five in the 240mg to 120mg cohort. Sixteen (22%) patients had partial remission or better, and 21 (29%) patients had stable disease. Median time to response was 56 days, median duration of response was 39 days. Median overall survival was 126 days; 175.5 days for the 120mg cohort and 88 days in the 240mg to 120mg cohort.¹⁹

1.1.4.3 Safety Results from the OPAL study¹⁹

The most common AEs according to two dosing schedules from the OPAL are summarized in Table 2. The most common adverse events were diarrhea, edema, fatigue, and dyspnea. Most common grade 3-4 side effects were febrile neutropenia, fatigue, and thrombocytopenia.

Table 2: Most Common Adverse Events Observed in >20% of Subjects

	Tosedostat 120 mg (n=38)			Tosedostat 240 mg to 120 mg (n=35)		
	All	Grade 3-4	Grade 5	All	Grade 3-4	Grade 5
Patients with at least one adverse event	38 (100%)	21 (55%)	13 (34%)	35 (100%)	16 (46%)	17 (49%)
Diarrhea	20 (53%)	2 (5%)	0	22 (63%)	1 (3%)	0
Peripheral edema	18 (47%)	0	0	22 (63%)	0	0
Fatigue	16 (42%)	7 (18%)	0	20 (57%)	8 (23%)	0
Dyspnea	16 (42%)	5 (13%)	0	14 (40%)	7 (20%)	0
Nausea	13 (34%)	0	0	15 (43%)	0	0
Decreased appetite	12 (32%)	1 (3%)	0	15 (43%)	1 (3%)	0
Hypotension	12 (32%)	3 (8%)	0	14 (40%)	4 (11%)	0
Febrile neutropenia	13 (34%)	11 (29%)	0	13 (37%)	8 (23%)	2 (6%)
Dizziness	12 (32%)	0	0	13 (37%)	0	0
Cough	12 (32%)	0	0	11 (31%)	1 (3%)	0
Pyrexia	12 (32%)	2 (5%)	0	11 (31%)	0	0
Asthenia	9 (24%)	1 (3%)	0	11 (31%)	3 (9%)	0
Hypokalemia	10 (26%)	2 (5%)	0	10 (29%)	3 (9%)	0
Constipation	10 (26%)	0	0	7 (20%)	0	0
Insomnia	9 (24%)	1 (3%)	0	8 (23%)	0	0
Rash	9 (24%)	2 (5%)	0	8 (23%)	0	0
Pneumonia	8 (21%)	3 (8%)	1 (3%)	9 (26%)	3 (9%)	3 (9%)
Vomiting	8 (21%)	0	0	8 (23%)	0	0
Thrombocytopenia	8 (21%)	8 (21%)	0	8 (23%)	8 (23%)	0

Serious adverse events are summarized in table 3. Most commonly reported serious adverse events were febrile neutropenia, disease progression, atrial fibrillation, pneumonia, pyrexia, and cardiac failure. In the study, discontinuation for tosedostat-related toxicity occurred in 14 (19%) of patients; 9 in 120mg cohort and 5 in the 240mg to 120mg cohort. There were five adverse events with outcome of death possibly related to tosedostat; three in the 120mg cohort, and two in the 240mg cohort. The adverse events were acute hepatitis, respiratory failure, pneumonia, atrial fibrillation, and left ventricular dysfunction.

Table 3: Serious adverse events occurring in $\geq 3\%$ of Subjects

	Tosedostat 120 mg (n=38)	Tosedostat 240 mg to 120 mg (n=35)
Patients with at least one serious adverse event	32 (84%)	30 (86%)
Febrile neutropenia	9 (24%)	12 (34%)
Disease progression	6 (16%)	5 (14%)
Atrial fibrillation	1 (3%)	5 (14%)
Pneumonia	1 (3%)	5 (14%)
Pyrexia	3 (8%)	1 (3%)
Cardiac failure, congestive	1 (3%)	2 (6%)
Cellulitis	2 (5%)	1 (3%)
Dyspnoea	1 (3%)	2 (6%)
Multiorgan failure	2 (5%)	1 (3%)
Rectal hemorrhage	0	3 (9%)
Respiratory failure	3 (8%)	0

1.1.4.4 Tosedostat with Azacitidine

Tosedostat was studied in combination with azacitidine in older patients with AML or high-grade MDS.¹⁹ This was a phase I/II trial of older, relapsed/refractory AML or high-risk MDS patients having failed prior hypomethylating agents. All subjects received tosedostat 120mg orally once daily for 28 day cycles with azacitidine at 50mg/m² or 75mg/m² for 7 days per cycle. There were 10 subjects enrolled. Median age of the subjects was 73, with majority with antecedent MDS and complex cytogenetics. 6 subjects were evaluable for response with 50% overall response rate: 2 subjects with morphologic leukemia free state, 1 with partial remission, 1 with stable disease, and 2 with progressive disease. 4 subjects discontinued prior to completion of cycle 1 for reasons other than study-drug related toxicity or progressive disease. The most common non-hematologic grade 3 or higher toxicities regardless of attribution included lung infection (4/10), wheezing (2/10), and somnolence (2/10). One fatal acute coronary event on cycle 2, day 2 of tosedostat 180mg/m² and azacitidine 75mg/m² was considered possibly related to the drug.

1.1.4.3 Safety Results from the OPAL study¹⁹

1.2 DOSE RATIONALE

In study CHR-2797-002, described above, the optimal dose of tosedostat was determined to be

130 mg once daily. Interpolation of the relationship between dose of tosedostat and PK parameters (Cmax, AUC), indicates little or no difference between doses of 120 and 130 mg. There were increased cardiovascular events with higher dosing schedules, including atrial arrhythmias. Therefore, for this study, 120 mg was chosen to provide the safest and most convenient dosing for subjects.

1.3 SUMMARY AND STUDY RATIONALE

The prognosis of MDS patients refractory to or relapsed after hypomethylating agents is poor and there is no effective therapy in this setting. There is an urgent need for novel compounds and treatment strategies for these patients. Tosedostat is a novel aminopeptidase inhibitor, which in preclinical experiments has shown potent activity in both *in vitro* and *in vivo* cancer models as a single agent. Early clinical trials mainly in AML demonstrated that it is safe and well tolerated, and has activity in refractory and relapsed AML patients. This study aims to evaluate the efficacy of tosedostat in MDS patients refractory to hypomethylating agents.

2 STUDY OBJECTIVES

Primary Objective:

The primary objective of the study is to evaluate the safety and efficacy of tosedostat in patients with myelodysplastic syndrome who have relapsed after or are refractory or intolerant to azacitidine or decitabine. The primary endpoint for patients is overall survival.

Secondary Objectives:

The following secondary endpoints will be evaluated:

- Hematological improvements (erythroid response [ER], platelet response [PLR] and neutrophil response [NR]) according to 2006 IWG criteria (Appendix 3), including reduction in RBC and/or PLT transfusion needs
- Overall response (complete remission [CR], partial remission [PR], bone marrow complete response [BMCR], and stable disease [SD] according to 2006 International Working Group (IWG) criteria, including, among responders, the distribution of time to response and the duration of response. (Appendix 3)
- Improvements of cytogenetics as evaluated by the change in aneuploidy in BM according to 2006 IWG criteria
- Safety and tolerability of tosedostat
- Time to AML transformation

3 INVESTIGATIONAL PLAN

3.1 CLINICAL STUDY DESIGN AND PLAN

This is a single-center, open label, phase II study of clinical activity of tosedostat in adult patients with MDS who have failed prior hypomethylating agent-based therapy. In this study, approximately 80 patients (80 patients;) will be enrolled at Weill Cornell Medical College. The dose of tosedostat will be 120 mg once a day continuously for each 28 day treatment cycle.

The dose of tosedostat should be taken orally with a glass of water after food preferably in the morning at about the same time every day to ensure an even dose interval.

Patients will be assessed for disease response every two cycles as defined in the protocol. If patient has no response as defined by the protocol after two cycles, azacitidine 75 mg/m² SC or IV for 5 days may be combined with tosedostat, at the investigator's discretion.

Subjects will be permitted to interrupt tosedostat treatment, to a maximum of 14 days, under circumstances described in Section 6.5. If a subject requires multiple, or prolonged (greater than 14 days) study medication interruptions, the principal investigator will be consulted for a discussion on the subject's continued participation in the study. Investigators are encouraged to avoid unnecessary subject withdrawal. Late response to therapy has been seen in earlier trials, particularly in those who have shown at least stabilization of disease. However, the safety of the subject is paramount and subject's right to withdraw at any time is absolute.

3.1.1 Screening (Study Day -14 to Day 1)

Initiate and complete screening activities within 14 days before Cycle 1, Day 1 treatment, with the exception that informed consent may be obtained within 28 days before Cycle 1, Day 1.

3.1.2 Treatment (Cycle 1, Day 1 through End-of-Treatment Visit)

This period begins on the day the patient first receives tosedostat and ends at the End-of-Treatment Visit.

3.1.3 Follow-up

After completion of the End-of-Treatment Visit, all patients are followed up for 30 days.

3.1.4 Clinical Study Endpoints

The primary endpoint the study is to evaluate the safety and efficacy of tosedostat in patients with myelodysplastic syndrome who have relapsed after or are refractory or intolerant to azacitidine or decitabine. The primary endpoint for patients is overall survival.

The following secondary endpoints will be evaluated:

- Hematological improvements (erythroid response [ER], platelet response [PLR] and neutrophil response [NR]) according to 2006 IWG criteria (Appendix 2), including reduction in RBC and/or PLT transfusion needs
- Overall response (complete remission [CR], partial remission [PR], bone marrow complete response [BMCR], and stable disease [SD] according to 2006 International Working Group (IWG) criteria, including, among responders, the distribution of time to response and the duration of response (Appendix 2). All responses of CR must be confirmed 4 weeks after achievement.
- Improvements of cytogenetics as evaluated by the change in aneuploidy in BM according to 2006 IWG criteria
- Safety and tolerability of tosedostat

- Time to AML transformation

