4.3 DURATION OF CLINICAL STUDY

Enrollment in this clinical study is expected to be completed in approximately 24 months, and the total study duration, including the 30-day follow up period, will be approximately 36-48 months. Patients have up to 4 cycles of treatment to achieve a response to tosedostat; responding patients may continue treatment indefinitely, at the discretion of the treating investigator, in collaboration with the sponsor.

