Patients with a documented response of CR, PR, hematologic improvement or stable disease at the end of Cycle 2 may be eligible to continue treatment indefinitely with tosedostat, at the discretion of the Investigator.. Study visits during Cycles 2+ have a 2-day window. Patients must have returned to at least baseline hematological parameters at the start of each cycles unless investigator deems cytopenias are secondary to underlying disease, and all drug-related non-hematological toxicities must have resolved to < grade 2.

5.2.2.1 *Day 1*

- Recording of any changes to medical history since the Screening Visit

- Recording of baseline signs and symptoms
- Physical examination, including assessment of extramedullary disease
- Assessment of ECOG performance status
- Vital signs, including body temperature (°C), pulse rate and systolic and diastolic blood pressures, weight (kg), and body surface area
- Collect blood samples for hematology, troponin I, b type natriuretic peptide, coagulation, and blood chemistry (blood samples may be omitted if obtained within 7 days)
- Collect urinalysis (may be omitted if obtained within 7 days)
- Perform 12-lead ECG
- Transthoracic echocardiogram, only if patient has been off of tosedostat for more than 2 weeks since prior cycle
- Recording of concomitant medications and significant non-drug therapies including blood product transfusions
- Assess and record of AEs
- Examination of subject treatment diary and return of unused tosedostat
- Dispense tosedostat

5.2.2.2 *Days 8, 15, 22*

- Physical examination, including assessment of extramedullary disease
- Vital signs, including body temperature (°C), pulse rate and systolic and diastolic blood pressures, weight, and body surface area
- Collect blood samples for hematology, chemistry, troponin I, b-type natriuretic peptide
- Perform 12-lead ECG
- Recording of concomitant medications and significant non-drug therapies including blood product transfusions
- Recording of AEs

5.2.2.3 *Days 28*

- Physical examination, including assessment of extramedullary disease
- Vital signs, including body temperature (°C), pulse rate and systolic and diastolic blood pressures, weight, and body surface area
- Collect blood samples for hematology, chemistry, troponin I, b-type natriuretic peptide
- Perform 12-lead ECG
- Transthoracic echocardiogram
- Recording of concomitant medications and significant non-drug therapies including blood product transfusions
- Recording of AEs

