5.7.4 Criteria for Protocol-Defined Required Discontinuation of Treatment

- Discontinue treatment with tosedostat if patients experience any of the following:
- Do not achieve CR, PR, hematologic improvement, or bone marrow remission after four cycles of treatment with tosedostat alone or 4 cycles of azacitidine if azacitidine is added to tosedostat.
- Experience disease progression
- Develop an intercurrent illness that prevents further treatment with tosedostat
- Develop unacceptable/intolerable AE(s)
- Withdraw from the clinical study
- Become pregnant
- Receive other systemic cancer therapy or protocol-prohibited medications
- Have general or specific changes that render the patient unsuitable for further treatment with tosedostat, in the judgment of the Investigator

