7.2 EFFICACY MEASURES

Primary and secondary endpoints include evaluation of efficacy by determination of the number of patients who achieve a response (i.e. CR, PR, stable disease, disease progression, or hematologic improvement). Response will be evaluated every 2 cycles or more frequently at the discretion of the investigator. Determination of disease response is based on the 2006 IWG response criteria (see Appendix 3).

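### Overall response, a secondary endpoint, lists stable disease as a component, which conflicts with the response criteria and treatment rules and puts stable disease among the responders

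*Combined protocol and SAP*

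**What the plan says.** The synopsis, section 2 and section 3.1.4 share one secondary endpoint: "Overall response (complete remission [CR], partial remission [PR], bone marrow complete response [BMCR], and stable disease [SD". The same sentence asks for the distribution of time to response and the duration of response in responders. It gives no separate definition of a responder.

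Two other places use response in a way that takes in SD:
- Section 5.2.2 speaks of "Patients with a documented response of CR, PR, hematologic improvement or stable disease at the end of Cycle 2" as possibly eligible to continue.
- Section 7.2 lists the responses a patient may achieve as "i.e. CR, PR, stable disease, disease progression, or hematologic improvement".

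The rest of the protocol points the other way:
- Appendix 2 defines SD as not reaching PR, without progression for more than 8 weeks. Its loss-of-response definitions cover relapse after CR or PR, and progression or relapse after hematologic improvement. None covers SD.
- Section 5.2.3 requires confirmation of CR and PR at 4 weeks and of hematologic improvement at 8 weeks. It asks for none for SD.
- Section 5.7.4 requires tosedostat to stop in patients who "Do not achieve CR, PR, hematologic improvement, or bone marrow remission after four cycles of treatment with tosedostat alone" (or after four cycles of azacitidine, if added). SD is not on that list. Section 4.3 agrees: "Patients have up to 4 cycles of treatment to achieve a response to tosedostat", and responders may then continue.
- Section 3.2 names SD without hematologic improvement after two cycles as the group for added azacitidine. Section 6.3, which implements this, is headed as an addition for non-response.

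Section 8 plans frequencies and percentages for proportions defined earlier and names no responder set.

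**The concern.** As written, the endpoint makes a responder of a patient whom Appendix 2 places below PR, whom 6.3 treats as a candidate for azacitidine because of non-response, and whom 5.7.4 takes off treatment at four cycles.

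Three summaries depend on the responder set: any pooled overall response rate, time to response, and duration of response. If SD counts, the rate describes disease control rather than response. Duration of response has no defined end event for the SD patients. Time to response for them would largely reflect the visit schedule, because SD needs more than 8 weeks without progression and the first scheduled response assessment is at the end of cycle 2. A patient who starts azacitidine while in SD would also already be a responder, so a later CR or PR would not set the time to response.

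The trial is open-label and single-arm, so the set should be fixed before the data are seen.

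**Working it through.** **1. Does the SD-inclusive definition work inside the protocol?** Sections 3.1 and 6.3 allow azacitidine after two cycles for patients without a response. If SD is a response, those patients are neither CR, PR, marrow CR nor SD, so in practice they have progressed. Section 5.7.4 already requires progressors to stop tosedostat. Almost nobody would be left, and the group that 3.2 names (SD without hematologic improvement) would be shut out. The treatment rules work only if SD is not a response.

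**2. Timing.** Two cycles are 2 × 28 = 56 days = 8 weeks, the point at which Appendix 2's requirement of more than 8 weeks is only just coming due. The first SD time would therefore sit at or after the first scheduled assessment.

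**3. The overall response rate quoted in the background.** Section 1.1.4.4 states: "6 subjects were evaluable for response with 50% overall response rate: 2 subjects with morphologic leukemia free state, 1 with partial remission". The other three patients were 1 SD and 2 progressive disease.
- SD excluded: (2 + 1)/6 = 3/6 = 50%, which reproduces the quoted figure.
- SD included: (2 + 1 + 1)/6 = 4/6 = 66.7%, which does not.

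This shows how the term is used in the background. It is another study's rate and does not bind this endpoint.

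**4. Size, from the background studies.** For OPAL, section 1.1.4.2 reports "Sixteen (22%) patients had partial remission or better, and 21 (29%) patients had stable disease"; Table 2 gives n = 38 + 35 = 73. For the four MDS patients in CHR-2797-002, "one subject met the criteria of stable disease and another subject reached a partial response". The OPAL categories are taken as mutually exclusive.

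| Source | SD excluded | SD included | Change in points | SD share of responders |
|---|---|---|---|---|
| OPAL (AML) | 16/73 = 21.9% | 37/73 = 50.7% | 28.8 | 21/37 = 56.8% |
| Azacitidine combination | 3/6 = 50.0% | 4/6 = 66.7% | 16.7 | 1/4 = 25% |
| CHR-2797-002, MDS only | 1/4 = 25% | 2/4 = 50% | 25 | 1/2 = 50% |

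**5. Scaled to 80 patients (illustration, not prediction).**
- Patients changing status: 0.167 × 80 = 13.3; 0.25 × 80 = 20; 0.288 × 80 = 23.0. That is 13 to 23 of 80.
- At OPAL rates, SD excluded: 0.219 × 80 = 17.5, taken as 18/80 = 22.5% (exact 95% CI 13.9% to 33.2%).
- At OPAL rates, SD included: 0.507 × 80 = 40.5, taken as 41/80 = 51.3% (exact 95% CI 39.8% to 62.6%).
- Range: with PR or better at 22% and an assumed SD rate of 10% to 40%, the rate including SD runs from 26/80 = 32.5% to 50/80 = 62.5%, against 18/80 = 22.5% without it.

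**The case against.** The best defence is that overall response is only a heading for IWG categories to be tabulated one by one. Section 8 refers to proportions in the plural, plans them descriptively, and sets no pooled rate, target or test. The list in 7.2 includes disease progression, so response there plainly means an assessment category. Sections 3.2, 5.2.2 and 5.7.4 are treatment rules, not analysis definitions. Confirmation in 5.2.3 and the relapse rules in Appendix 2 already lean towards leaving SD out of the timing summaries.

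Much of this stands. Separate category counts are unaffected, and 7.2 is weak evidence that SD was meant as a response. But the endpoint sentence still asks for two summaries in responders and gives no set other than a list containing SD. That the rest of the protocol leans the other way is what makes the sentence wrong as written. Nor is Appendix 2's wording for SD decisive alone: marrow CR can also fall short of PR and likewise has no relapse rule.

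A reader might infer more than the documents support:
- That the two intervals in the illustration, which do not overlap, show a real difference. They describe nested definitions in the same patients, so overlap has no inferential meaning.
- That earlier tosedostat results are the only context for response here. Section 1.1.3 also gives bestatin results in MDS (10 of 13 patients; 7% of 71), and no section plans a comparison with earlier studies.
- That the plan commits to a rate near 51%. No pooled rate is expressly planned, OPAL is an AML study, and its SD criterion is not given.

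**Conclusion.** The concern holds for a descriptive secondary endpoint. Read literally, the overall response definition counts SD, against Appendix 2, 5.2.3, 5.7.4 and 3.2 with 6.3. It affects any pooled response rate and the time-to-response and duration-of-response summaries. On the background proportions, 13 to 23 of 80 patients would change status; at the OPAL proportions most responders would be SD, so the timing medians would mainly describe SD. These sizes assume that AML results, or results from 4 and 6 patients, carry over to this population, so they show scale only.

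Overall survival, the sample size of 80, its power and the primary test do not depend on the response definition. The azacitidine group is also not left open in substance: 3.2 and 5.7.4 together identify it. This is a wording correction worth making before analysis.

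**What to change.** 1. In the synopsis, section 2 and 3.1.4, remove SD from overall response and define it as CR + PR + marrow CR.
2. Report SD as its own category. If a rate including SD is wanted, call it disease control.
3. Keep hematologic improvement as its own secondary endpoint. State that it counts as response for the treatment rules in 6.3 and 5.7.4 but is reported separately from overall response.
4. State, there and in section 8, that time to and duration of response are computed in the CR/PR/marrow CR set. Since Appendix 2 has no relapse rule for marrow CR, say which event ends one.
5. In 7.2, take stable disease and disease progression off the list of responses achieved. For consistency, 5.2.2 should name SD apart from the responses.

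The cost is protocol wording and the layout of the response table. Each category is already assessed under Appendix 2, so no new data, visits or patients are needed.
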